6.2.3.2 Specimen Shipment

Sputum specimens in closed vials inside of a sealed bag are transported by NICD courier to the central NICD laboratory according to standard NICD procedures. This occurs 1-2 times on each weekday, and the timing is variable by clinic. Specimens are kept at 4°C in a cooler until reaching the laboratory. Specimens for WGS will be transported by NICD courier to the NICD headquarters in Johannesburg as above, on a bi-weekly basis by courier.

7 STUDY SCHEDULE

7.1 Screening and Enrollment

Within Limpopo Province, we will have two study sites, one in Vhembe and one in Capricorn district, while in Tshwane municipality we will have one site covering Soshanguve and surrounding areas. Within each site, we will seek to enroll all consecutive patients meeting the eligibility criteria. Potential eligibility will be assessed weekly review of the presumptive TB and TB treatment registers at each study facility, in close collaboration with healthcare staff in each hospital. We will approach all potentially eligible participants for informed consent at their treatment location within two weeks of diagnosis, making phone calls and/or home visits as necessary to contact participants who have been lost to follow-up between diagnosis and treatment initiation.

All individuals present at the household at the time of a household study visit will be considered eligible for enrollment as contacts, and all adults approached during the timing of the bioethics sub-study will be considered eligible for enrollment into that sub-study.

7.2 Enrollment/Baseline, if applicable

See above.

7.3 Follow-up and Final Visits, if applicable

Not applicable, unless the participant is a household contact who is diagnosed with TB or selected for the bioethics sub-study. For household contacts, we will perform a follow-up visit to relay results and refer for treatment, however no other study-specific procedures will be performed at this visit. For the bioethics sub-study, all procedures will be completed during a single follow-up visit (during which no personal identifiers will be recorded).

7.4 Early Termination Visit, if applicable

Not applicable.

7.5 Criteria for Discontinuation or Withdrawal of a Subject (or a Cohort), if applicable

Participants may withdraw from the study voluntarily at any time, but there are no further criteria for discontinuation or withdrawal.

8 ASSESSMENT OF OUTCOME MEASURES

8.1 Specification of the Appropriate Outcome Measures

8.1.1 Primary Outcome Measure

The effectiveness of contact tracing, measured as the number of secondary cases identified and started on treatment per index case, comparing households in the novel arm to households in the standard arm.

8.1.2 Secondary Outcome Measures

- 1. The TB prevalence ratio, comparing highly mobile to less mobile individuals, measuring mobility on two scales (neighborhood/intra-urban and regional/intra-national).
- 2. Relative acceptability of each novel strategy, compared against routine contact investigation. We will create a continuous score from the acceptability interview questions (provided to a randomly selected 15% of the population), with a higher score indicating greater acceptability of the contact tracing strategy.
- 3. Feasibility of each strategy as the proportion of potentially eligible index cases for whom a household visit was conducted.
- 4. Relative fidelity of each novel strategy using a process checklist for each index case and household, including whether the household visit was offered and accepted, whether the visit was attempted, whether the visit was successful (i.e., enrolled at least one contact), whether symptom screening and sputum collection were completed and whether newly identified TB cases were notified and referred for treatment.
- Sustainability of each novel strategy by reporting the primary outcome and fidelity measures according to six-month time period over the course of the study.
- 6. Incremental cost-effectiveness ratio for each novel strategy. defined as (cost of contact tracing strategy 2 cost of strategy 1)/(effectiveness of strategy 2 effectiveness of strategy 1), where effectiveness is modeled as the number of disability-adjusted life years (DALYs) averted by the intervention. The primary cost-effectiveness measures will be the incremental cost per DALY averted using novel strategies (holiday and off-hours contact tracing) compared to routine contact tracing in each setting separately.

7. Experiences of inconvenience, attitudes toward confidentiality, motivation to participate, and preferences for disclosure, assessed through both thematic analysis of in-depth interviews and focus group discussions and quantitative analysis of discrete choice experiments and best-worst scaling.

9 SAFETY ASSESSMENT AND REPORTING

9.1 Definition of Adverse Event (AE)

As our intervention is the implementation and observation of routine South African standard of care (contact tracing of newly identified TB cases), we do not anticipate any medical adverse events which may occur as a result of this research study. Therefore, AEs (including SAEs) will not be recorded and reported for this study.

9.2 Definition of Serious Adverse Event (SAE)

N/A-see 9.1 "Definition of Adverse Event"

9.3 Reporting Procedures

N/A-see 9.1 "Definition of Adverse Event"

9.3.1 Serious Adverse Event Detection and Reporting

N/A-see 9.1 "Definition of Adverse Event"

9.3.2 Reporting of Pregnancy

This is a cross-sectional study which makes no attempt to exclude pregnant women. Pregnancy does not represent a complication within the context of this research study. Pregnancy status of any enrolled participant will be documented.

9.3.3 Procedures to be Followed in the Event of Abnormal Laboratory Test Values or Abnormal Clinical Findings

TB cases detected through this study are referred for care to their closest public health clinic for further evaluation and treatment, according to the South African standard of care. As TB is a measured outcome of this study, and detection of TB is the overall goal, it is not considered an AE or SAE.

9.3.4 Type and Duration of the Follow-up of Subjects After Adverse Events

N/A-see 9.1 "Definition of Adverse Event"

10 CLINICAL MONITORING STRUCTURE

Site monitoring is conducted to ensure that the human subject protections, study and laboratory procedures, study intervention administration, and data collection processes are of high quality and meet sponsor, ICH/GCP guidelines and applicable regulations, and that the study is conducted in accordance with the protocol, protocol-specific MOP and applicable sponsor standard operating procedures. DMID, the funder of the project, or its designee may conduct site-monitoring visits.

Site visits may be made at standard intervals and may include, but are not limited to, review of regulatory files, informed consent forms, laboratory reports, and protocol and GCP compliance. Site monitors will have access to the study site, study personnel, and all study documentation. Study monitors will meet with site principal investigators to discuss any problems and actions to be taken and document visit findings and discussions.

11 STATISTICAL CONSIDERATIONS

11.1 Study Outcome Measures

Primary Outcome Measure:

Our primary effectiveness outcome will be the ratio of the number of secondary TB cases identified and started on treatment per index case, comparing index cases allocated to the novel strategy (off-peak screening in Soshanguve and holiday screening in Limpopo) to those receiving standard contact investigation.

Secondary Outcome Measures:

- The TB prevalence ratio, comparing highly mobile to less mobile individuals, measuring mobility on two scales (neighborhood/intra-urban and regional/intra-national). For the former, we will estimate the number of kilometers traveled on a daily basis (secondary analysis: amount of time spent in transit), truncating long excursions at 50km (one hour).
- 2. TB strain relatedness using maximum likelihood transmission trees. We will integrate TB natural history, epidemiological, and WGS-derived phylogenetic data into a statistical modeling framework to draw probabilistic conclusions about the likelihood of transmission between persons. "Transmitters" will be defined as individuals from whom at least one secondary case most likely originated.
- Relative acceptability of each novel strategy, compared against routine contact investigation. We will measure acceptability of the intervention among index cases and contacts using a short questionnaire given to a randomly selected participant at a randomly selected 15% of the households visited. The interview will cover acceptability of the visit timing, notification, visit activities (TB screening, HIV testing) and study team interaction among others.
- 4. Feasibility of each strategy as the proportion of potentially eligible index cases for whom a household visit was conducted. We will also record all reasons why visits were unable to be conducted (e.g. could not find household, no one ever home, visit not conducted during expected off-peak period).
- 5. Relative fidelity of each novel strategy using a process checklist for each index case and household, including whether the household visit was offered and accepted, whether the visit was attempted, whether the visit was successful (i.e.,

enrolled at least one contact), whether symptom screening and sputum collection were completed and whether newly identified TB cases were notified and referred for treatment.

- 6. Sustainability of each novel strategy by reporting the primary outcome and fidelity measures according to six-month time period over the course of the study.
- Incremental cost-effectiveness ratio for each novel strategy. defined as (cost of contact tracing strategy 2 – cost of strategy 1)/(effectiveness of strategy 2 – effectiveness of strategy 1), where effectiveness is modeled as the number of disability-adjusted life years (DALYs) averted by the intervention. The primary cost-effectiveness measures will be the incremental cost per DALY averted using novel strategies (holiday and off-hours contact tracing) compared to routine contact tracing in each setting separately.
- 8. Experiences of inconvenience, attitudes toward confidentiality, motivation to participate, and preferences for disclosure, assessed through both thematic analysis of in-depth interviews and focus group discussions and quantitative analysis of discrete choice experiments and best-worst scaling.

11.2 Sample Size Considerations

We estimate our sample size based on the assumption that 3% of household contacts will have tuberculosis (half the 6% prevalence seen in a previous study led by [name]),⁶⁴ and that an average of two contacts per case will be screened in the routine arm (based on our ongoing trial in Limpopo). Thus, in the routine arm, we anticipate a mean of 0.06 secondary cases per index case. Given the additional complexity of holiday-time or off-peak screening, we power our analysis under the *a priori* belief that such interventions will not be reasonably implemented unless they result in a yield that is twice that under routine contact investigation. Assuming an average of two to five contacts per household and a high (0.68) between-household coefficient of variation of the outcome as found in ⁶⁴, a comparison of n=1600 households (index cases) in the routine arm and 800 households (index cases) in the novel arm would have more than 99% power to detect this difference. If only half of the expected index cases are enrolled, the minimum power (two contacts per household) would be 84%. A maximally conservative estimate of sample size – assuming complete clustering of these cases at the household level, two contacts per household, and only 50% as many household cases.

We have selected our sample size to give more than 90% power to detect this most conservative difference. The table below provides estimates of our power to detect a statistically significant difference in the primary outcome.

Table. Power calculations. The power to detect each difference is given in italics; the primary comparison is between finding 0.06 secondary cases per index case in the routine arm and 0.12 in the novel screening arm.

		Mean number of secondary cases per index case, novel approach										
		0.08	0.1	0.12	0.18	0.24						
un er of dary per per case case ine	0.02	>0.99	>0.99	>0.99	>0.99	>0.99						
	0.04	0.99	>0.99	>0.99	>0.99	>0.99						
Me numk secor secor case: index , rou , rou	0.06	0.54	0.97	>0.99 (primary)	>0.99	>0.99						
	0.08	-	0.44	0.93	>0.99	>0.99						

Randomization

Randomization will be performed using computer-generated random permuted blocks of varying sizes, with an allocation ratio of 2 (routine):1 (novel: holiday or off-peak). Randomization will be conducted separately for Limpopo and Soshanguve and surrounding areas (i.e., two separate randomization sequences will be generated for each site); and within Limpopo, randomization will be further stratified by district, thus ensuring 2:1 allocation within each district as well. The randomization schedules will be uploaded into the REDCap system, which will automatically output an allocation every time a new consented patient is added and the interview is completed. In Limpopo, randomization will be performed throughout the year; those patients who are allocated to holiday timing will undergo household contact investigation during Easter if they are enrolled between February 1 and the end of the two-week Easter holiday, whereas those patients enrolled between the end of the Easter holiday and December 31 will undergo contact investigation during Christmas.

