6 STUDY PROCEDURES/EVALUATIONS

6.1 Study Procedures

Recruitment

Within Limpopo Province, we will have two study sites, one in Vhembe and one in Capricorn district and these sites will recruit participants from a total 12 hospitals. In Tshwane (across both North West and Gauteng provinces) we will have one site in Soshanguve, and this will recruit participants from 33 clinics and two district hospitals. Within each site and clinic/hospital, we will seek to enroll all consecutive patients meeting the following inclusion criteria: (a) diagnosed with pulmonary TB at one of the study health facilities (including microbiological and/or chest x-ray diagnosis); (b) plan to pursue treatment within the study district; (c) willingness to provide informed consent and comply with study procedures. We will also include those patients who are recently deceased from the hospital register. Eligible participants will be identified by weekly review of the presumptive TB and TB treatment registers in each location, also in close collaboration with healthcare staff in each study health facility. We will approach all potentially eligible participants for informed consent at their treatment location within two weeks of diagnosis, making phone calls as necessary to contact participants who have been lost to follow-up between diagnosis and treatment initiation. For patients who are recently deceased, the next of kin will be contacted and asked if they can consent for the patient's information to be included in the study. Next of kin will also be asked to provide temporary consent for index patients who are too ill to consent at the time of enrollment. (These patients will be reapproached for consent once they have recovered to the extent of being able to complete the consent process.) After providing informed consent, participants will be randomized via a computer-generated algorithm to either routine or novel (holiday or off-peak) household contact investigation. Of note, participants who after consent and randomization, decline to accept household contact investigation - or who cannot be located at home at the time of home visit, will be included in the primary analysis as not resulting in a secondary case detected. Recruitment will be continued until 2400 participants are enrolled in each arm (expected to be completed within 28 months). For the bioethics sub-study, eligible participants will include all individuals who were enrolled in the parent study and completed follow-up for the primary outcome (including those who declined or were ineligible to participate in household contact investigation). For this sub-study, we will enroll consecutive eligible participants in each district until our desired sample size (~64 index cases and ~64 evaluable household contacts from each district) has been attained.

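### The claim of more than 90% power for the worst-case scenario fails if its three conditions are cumulative (about 0.60–0.68 at 1600:800), and the unfinished scenario sentence does not say whether they are

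*Combined protocol and SAP*

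**What the plan says.** Section 11.2 builds the base case on the "assumption that 3% of household contacts will have tuberculosis" and on the expectation that "an average of two contacts per case will be screened in the routine arm", so that "we anticipate a mean of 0.06 secondary cases per index case". The target effect is a doubling: the novel strategies would not reasonably be adopted "unless they result in a yield that is twice that under routine contact investigation". The sample is "a comparison of n=1600 households (index cases) in the routine arm and 800 households (index cases) in the novel arm", and power for 0.06 versus 0.12 is given as above 99%, or at least 84% if only half the index cases are enrolled.

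The section then introduces a maximally conservative estimate, "assuming complete clustering of these cases at the household level, two contacts per household, and only 50% as many household cases". The sentence ends there, with no rates and no result. The next sentence reads "We have selected our sample size to give more than 90% power to detect this most conservative difference". The power table has no row for this scenario, and neither alpha nor sidedness is stated.

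Section 11.4 specifies an unpaired t-test and a separate analysis in each setting, so each test has 1600 routine and 800 novel index cases.

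**The concern.** The sentence explains how the sample size was chosen and presents the trial as robust to the worst case. Taken as a list joined by a conjunction, the scenario applies complete clustering and, in addition, a halving of household cases. Each of these alone uses up most of the spare power at 1600:800, and both together should take power well below 90%.

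At stake is how a null result in either setting would be read. If yield turns out low and concentrated in few households, a reader relying on this sentence would put the chance of missing a true doubling below 10%. On the cumulative reading it is about 32–40%.

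**Working it through.** **Inputs.** From Section 11.2: 3% of contacts with TB in the routine arm, two contacts per index case, doubling in the novel arm, 1600:800, and between-household coefficient of variation 0.68 for the base case. From Section 11.4: unpaired t-test, settings analysed separately. Assumed because not stated: two-sided alpha of 5%.

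**Plan's base case first.** The standard cluster formula with m = 2 contacts and k = 0.68 has variance, summed over arms, of [p(1−p)/m + k²p²]/n:

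- Routine: (0.03×0.97/2 + 0.4624×0.0009)/1600 = 0.01497/1600
- Novel: (0.06×0.94/2 + 0.4624×0.0036)/800 = 0.02986/800
- SE = 0.00683; power = Φ(0.03/0.00683 − 1.96) = 0.992

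The figure above 99% is reproduced. At 800:400 the same formula gives 0.874, against the plan's 84%.

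**Turning the scenario into rates.** With two contacts and complete clustering, a household has either no cases or two. A mean of 0.06 then means 3% of households affected, and 0.12 means 6%. A t-test on such counts is equivalent to a comparison of household proportions.

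- *Cumulative reading:* these rates are halved again, giving 1.5% versus 3%.
- *Single-halving reading:* the 50% adds nothing further, leaving 3% versus 6%.

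**Formulas.** SE₁ = √[p₁(1−p₁)/n₁ + p₂(1−p₂)/n₂]. SE₀ = √[p̄(1−p̄)(1/n₁ + 1/n₂)], where p̄ is the weighted mean. Unpooled power = Φ(d/SE₁ − 1.96). Pooled power = Φ((d − 1.96·SE₀)/SE₁).

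*Cumulative, 1600:800.* d = 0.015, p̄ = 0.02, SE₁ = 0.00675, SE₀ = 0.00606.

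- Unpooled: Φ(2.22 − 1.96) = 0.60
- Pooled: Φ((0.015 − 0.01188)/0.00675) = 0.68

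*Single halving, 1600:800.* d = 0.03, p̄ = 0.04, SE₁ = 0.00942, SE₀ = 0.00849.

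- Unpooled: Φ(3.19 − 1.96) = 0.89
- Pooled: Φ((0.03 − 0.01663)/0.00942) = 0.92

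**Results, with simulation of the planned t-test.**

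| Households affected | Unpooled | Pooled | Welch t (simulated) | Student t (simulated) |
|---|---|---|---|---|
| 1.5% vs 3% | 0.60 | 0.68 | 0.62 | 0.68 |
| 3% vs 6% | 0.89 | 0.92 | 0.91 | 0.93 |

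One-sided 5% would raise the first row only to 0.72–0.77.

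**A check inside the plan.** Halving the case rate at full enrolment gives the same expected number of cases as halving enrolment at the full rate: 1600×0.03 = 800×0.06 = 48 in the routine arm, and 800×0.06 = 400×0.12 = 48 in the novel arm. The plan itself puts half enrolment at 84% without complete clustering. Adding complete clustering cannot bring that above 90%. This is supporting evidence only, since the 84% comes out at 0.87 by the formula above.

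**The case against.** The strongest reply is that 1.5% and 3% appear nowhere in the plan. The 50% could refer to the halving already made when 3% was taken as half of a previously observed 6%. It could also describe what complete clustering does, since two-case households number half as many as the cases. Either way the comparison is 3% versus 6% of households, and the planned t-test then has 0.91–0.93 power. The continuity-corrected size for 90% power on that reading is 1563:782, close to the chosen 1600:800. This stands: a reader might infer that the claim is simply false, and the documents do not support that, because the sentence is unfinished and prints no rates. Against it, this reading leaves the third listed condition with no work to do.

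A second reply is that the sample size could mean both settings together. At 3200:1600 the cumulative scenario has 0.90 (Welch) to 0.92 (pooled normal) power. But Section 11.2 quotes 1600:800 and Section 11.4 analyses the settings separately, so this is the weaker defence.

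A reader might also infer that the claim was carried over from a design with 2400 per arm, because Section 6.1 says "Recruitment will be continued until 2400 participants are enrolled in each arm" and 2400:2400 gives 0.94 for the cumulative scenario. The documents do not support this. 2400 is also 1600 + 800, the total per setting, so the word for arm may merely be loose, and several configurations exceed 90%.

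Finally, the designated primary comparison is 0.06 versus 0.12, whose power above 99% is reproduced. The disputed sentence concerns a sensitivity scenario.

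**Conclusion.** The concern holds conditionally. If the three conditions are cumulative, as listed, power at 1600:800 per setting is about 0.60–0.68 and the claim of more than 90% fails by some 22–30 percentage points. With complete clustering at the per-setting sample, the claim is recovered under the planned t-test only if the 50% is not a further halving. The plan does not say which reading is meant, so a reader cannot verify the sentence on which the sample size is said to rest.

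The result assumes two-sided 5%, exactly two contacts per household and a doubling of yield. It does not show that the trial is underpowered for its designated primary comparison.

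**What to change.** Complete the scenario sentence in Section 11.2 with the household rates in each arm, alpha and sidedness, and the test, and restate the power at 1600:800 per setting. Then choose one:

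- Keep all three conditions and state power of about 0.60–0.68 for 1.5% versus 3% of households.
- Delete the 50% condition and state about 0.91–0.93 for complete clustering at 3% versus 6% of households under the planned t-test.

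Do not claim more than 90% for the combined scenario. A row for the chosen scenario in the power table would let readers check it.

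The cost is protocol wording and, under the first option, a less favourable printed figure. No change to enrolment, allocation or analysis is needed.

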11.4 Analysis Plan

Primary Outcome:

Our primary effectiveness outcome will be the ratio of the number of secondary TB cases identified and started on treatment per index case in the novel strategy arm (off-peak screening in Soshanguve and holiday screening in Limpopo) compared to index cases receiving standard contact investigation. We will conduct separate analyses for each site (rural Limpopo and peri-urban Soshanguve). For the primary analysis we will conduct an unpaired t-test for the hypothesis that the difference between the number of secondary TB cases per index case is the same in the two study arms. A secondary analysis will be performed to adjust for index case demographics, socio-economic factors, self-reported health seeking behavior, and clinical characteristics such as HIV status and history of TB. As the majority of the index cases are expected to have no secondary cases, this will be conducted using a zero-inflated Poisson regression with robust standard errors to account for household and enrollment site clustering.

Secondary outcome measures:

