- 8. Experiences of inconvenience, attitudes toward confidentiality, motivation to participate, and preferences for disclosure. Outcome measures will be assessed via Likert scales which will be evaluated via multivariable regression, adjusting for demographic characteristics, district, study arm, and household characteristics (e.g., size). Responses will be dichotomized based on exploratory data analysis and conduct log-binomial regression, comparing these results to those of linear regression performed after assigning a numerical value to each response level. Our generic (e.g. unlabeled) discrete choice experiment (DCE) will be based on five different attributes (disclosure of index case TB status, routine vs off-peak evaluation, inclusion of routine HIV testing, use of official vs unmarked cars, provision of monetary reimbursement for time), each with two different levels. The DCE will utilize a fractional factorial design created to estimate the main effects alone. Results from the DCE for certain characteristics

will be compared against a double-bounded contingent valuation survey in which we will evaluate participants' willingness to accept household CI (with different characteristics) with and without monetary reimbursement of different levels (to compensate for household members' time).

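### The primary Limpopo t-test omits the district stratum used in randomisation: the test stays valid, but its standard error is slightly too wide

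*Combined protocol and SAP*

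**What the plan says.** **Randomisation (section 11.2).** Permuted blocks are used "with an allocation ratio of 2 (routine):1 (novel: holiday or off-peak", separately for Limpopo and for Soshanguve and surrounding areas. In addition, "within Limpopo, randomization will be further stratified by district, thus ensuring 2:1 allocation within each district as well". Section 6.1 (Recruitment) names the two Limpopo districts, Vhembe and Capricorn, with one study site in each. REDCap will "automatically output an allocation every time a new consented patient is added and the interview is completed", so the index interview comes before allocation.

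**Primary analysis (section 11.4).** "We will conduct separate analyses for each site (rural Limpopo and peri-urban Soshanguve"; districts are not separated. "For the primary analysis we will conduct an unpaired t-test" is the whole method, with no stratum term.

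**Adjusted secondary analysis of the same outcome (section 11.4).** It will "adjust for index case demographics, socio-economic factors, self-reported health seeking behavior, and clinical characteristics such as HIV status and history of TB", using "zero-inflated Poisson regression with robust standard errors to account for household and enrollment site clustering". Neither district nor household size appears in the covariate list.

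**Elsewhere in section 11.4.** The bioethics outcome (secondary outcome 8) is analysed "adjusting for demographic characteristics, district, study arm, and household characteristics (e.g., size". The fidelity outcome (secondary outcome 5) is adjusted for enrolment site.

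**The concern.** Stratified blocks force the 2:1 ratio within each district, so a difference in yield between Vhembe and Capricorn cannot bias the comparison of arms. The unstratified t-test still counts that difference as noise. Its standard error is then larger than the design warrants, and the analysis does not follow the randomisation. The loss should be most visible if enrolment falls short or the true effect is less than a doubling.

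A related question is household size. The plan builds its expected yield from contacts per case times prevalence (2 × 3% = 0.06, section 11.2), so size should predict the outcome. The plan adjusts a bioethics outcome for it but not the primary effectiveness outcome.

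**Working it through.** **Inputs from section 11.2.** Means of 0.06 (routine) and 0.12 (novel) secondary cases per index case; coefficient of variation 0.68; 1600 and 800 index cases per setting. The documents state neither alpha nor sidedness, so two-sided 5% is assumed.

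**Step 1: the plan's own power.** Variance per index case is V(μ) = μ + 0.68²μ².
- V(0.06) = 0.06 + 0.4624 × 0.0036 = 0.06166.
- V(0.12) = 0.12 + 0.4624 × 0.0144 = 0.12666.
- SE = √(0.06166/1600 + 0.12666/800) = 0.01403, and 0.06/0.01403 = 4.276.
- Power = Φ(4.276 − 1.96) = 0.990. The plan says more than 99%.
- At 800 and 400: SE = 0.01984, and power = Φ(3.024 − 1.96) = 0.856. The plan says 84%.

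Both agree closely enough to use this variance below.

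**Step 2: the cost of leaving out district.** Assume two equal districts whose routine yields average 0.06, with the novel strategy doubling yield in each. The between-district variance in an arm is (half the difference in yields)². The within-district variance is the average of V over the two districts. Each is divided by the arm size and summed over arms to give B and W. The ratio of unstratified to stratified SE is √((W + B)/W).

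| Routine yields (assumed) | Factor | Within: routine, novel | Between: routine, novel | W (×10⁻⁴) | B (×10⁻⁴) | SE ratio |
|---|---|---|---|---|---|---|
| 0.05 v 0.07 | 1.4 | 0.06171, 0.12684 | 0.0001, 0.0004 | 1.9712 | 0.0056 | 1.0014 |
| 0.04 v 0.08 | 2 | 0.06185, 0.12740 | 0.0004, 0.0016 | 1.9790 | 0.0225 | 1.0057 |
| 0.03 v 0.09 | 3 | 0.06208, 0.12832 | 0.0009, 0.0036 | 1.9920 | 0.0506 | 1.0126 |

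The unstratified SE is therefore 0.1% to 1.3% too wide. At a factor of 2, adjustment leaves power at 0.990 with full enrolment and moves it from 0.856 to 0.860 with half enrolment.

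**Step 3: simulation.** 4000 trials of 2400 index cases; districts differing twofold; mean 2 contacts with variance 4 (assumed).

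| True means | t-test | + district | + district and size |
|---|---|---|---|
| 0.06 v 0.06 (type I error) | 0.052 | 0.053 | 0.048 |
| 0.06 v 0.08 | 0.327 | 0.330 | 0.354 |
| 0.06 v 0.10 | 0.838 | 0.840 | 0.871 |
| 0.06 v 0.12 | 0.989 | 0.989 | 0.995 |

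The powers at 0.08 and 0.10 lie below the plan's table (0.54 and 0.97). That gap is a separate matter and does not come from the district stratum.

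**Step 4: household size.** Variance explained is (slope × SD of size)², subtracted from V(0.06) and V(0.12).
- If reported size equals the number screened, the slopes are 0.03 and 0.06. SD 1.5 explains 0.0020 and 0.0081, giving an SE ratio of √[((0.06166 − 0.0020)/1600 + (0.12666 − 0.0081)/800)/0.00019686] = 0.971. SD 2.0 explains 0.0036 and 0.0144, giving 0.947.
- If reported size is a looser proxy with mean 5 and SD 2 (assumed), the slopes are 0.06/5 = 0.012 and 0.12/5 = 0.024. Explained variance is 0.0006 and 0.0023, and the SE ratio is 0.992.

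The SE reduction is therefore about 1% to 5%.

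**The case against.** The strongest reply is that nothing is broken. The t-test holds its size, its slight conservatism is harmless, and power for a doubling is already about 99%. An unadjusted primary with an adjusted secondary analysis is a common choice. All of that stands, and it keeps the point small.

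It can also be said that enrolment-site clustering already covers district. This stands only in part. With one study site per Limpopo district, the term may well mean district, but cluster-robust errors would then rest on two clusters in Limpopo and one in Soshanguve. If it means hospital or clinic, it changes the standard error without taking the district difference out of the residual. Neither reading is a stratum term.

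A reader might go further and infer three things that the documents do not support:
- *That household size is used nowhere.* Secondary outcome 8 adjusts for it, and for district. The gap concerns the primary effectiveness outcome only.
- *That size is sitting in the baseline interview, free to use.* Section 6.1 does not list it among the interview items. Next of kin answer for deceased or very ill index cases, so some values may be missing or approximate. Teams recruit whoever is available, and visitors are eligible, so reported size need not match the number screened, least of all in the holiday arm.
- *That chance imbalance in size threatens the result.* With SD 1.5 to 2.0, the SE of the imbalance is SD × √(1/1600 + 1/800) = 0.065 to 0.087 people. At 3% prevalence that is about 0.002 to 0.003 cases against a target difference of 0.06, and the t-test's standard error already allows for it.

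**Conclusion.** The point holds as a minor one. The Limpopo stratum is missing from the primary test and from the covariates listed for the secondary model of the same outcome. The result is a standard error about 0.1% to 1.3% too wide, under assumed district yields differing by a factor of 1.4 to 3, equal district sizes and a doubling of yield in each district. In the simulation the loss is well under one point of power.

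This is not a validity error and does not undermine the sample size. The reason to act is that the analysis should follow the randomisation and doing so has no statistical drawback. The household-size addition is conditional on the item being recorded before allocation, and its 1% to 5% rests wholly on assumed distributions.

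**What to change.** - **Primary Limpopo analysis:** linear regression of secondary cases per index case on arm, with a district term and robust standard errors. Keep the unadjusted t-test as a supporting result.
- **Secondary model:** add district to the covariates, and state whether enrolment site means study site or health facility.
- **Conditional:** if household size is recorded in the index interview before allocation, prespecify it as a covariate for the primary effectiveness outcome in both settings, with a rule for missing values. Do not adjust for the number of contacts found at the visit: it arises after randomisation and is part of what the strategies are meant to change.

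The district changes cost a few lines of analysis-plan wording, since district is already known at randomisation. Household size would need a required interview field if it is not already collected, and it cannot be recovered as a baseline value for participants already allocated without it. All of this should be fixed before anyone sees outcome data by arm.
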